In the three groups of intraoperative blood oxygen changes (Table 2), without intubation and without muscle relaxants, the CO₂ content in the body is less than that of muscle relaxants, and there is no possibility of PaCO₂ ≥ 80mmHg. In the postoperative discomfort reaction (Table 3), 1 patient in group 1 and 3 had sore throat, and 1 patient in group 3 had difficulty breathing when he was interviewed in the recovery room. The side effects of postoperative nausea and vomiting (Table 4), each of the first group and the third group had nausea and vomiting. In the vital signs before, during and after the operation (Table 5), the heartbeat of the second group had an upward trend during the operation. In the surgical field of vision (Table 6), one in the first group affected the field of vision due to the appearance of congenital structures, one in the third group had an abnormal vocal cord structure that affected the field of vision, and the second group had no poor surgical field of vision. A questionnaire survey by the chief surgeon (Table 7) showed that the surgeons were satisfied with the surgical satisfaction of the three groups, but the pressure was higher when performing non-intubation and nerve block surgery.

Each group must collect 30 people, to compare the effects of intubation and non-intubation on the surgical field of vision and the changes in blood oxygen during the operation. At present, we have collected data on 29 patients. We anticipate that

needed 61 patient data. In order to achieve the accuracy and legibility of the number of statistical samples. And to explore the safety of laryngoscope microsurgery under non-intubation anesthesia.

B BACKGROUND AND PURPOSE

Importance and research status of this project at home and abroad, and indicate important documents ◦

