10. Yang SS, Wang N-N, Postonogova T, Yang GJ, McGillion M, Beique F, Schricker T. Intravenous lidocaine to prevent postoperative airway complications in adults: a systematic review and meta-analysis. British journal of anaesthesia 2020.

表單 G4

C METHODS AND STUDY PROCEDURE

We expect to treat patients from 20 to 80 years of age who need to undergo laryngoscope microsurgery and are divided into three groups, the first group: the intubation general anesthesia group, and the second group, the third group two non-intubation Anesthesia group.

Patients in the intubation general anesthesia group will receive intravenous anesthesia using target-controlled infusion (TCI) propofol and remifentanyl, and they will be given intravenous 0.2 mg glycopyrolate and 40 mg methylprednisolone and 5 mg midazolam. After losing consciousness, give cisatracurium 0.15mg/kg, and then perform endotracheal intubation (5.0-5.5, I.D. mm). After the endotracheal intubation is completed, it will be transferred to the respirator for positive pressure ventilation and maintained until the end of the operation.

[figure not shown]
Patients undergoing non-intubation anesthesia for laryngoscope microsurgery will use transnasal humidified rapid-insufflation ventilator exchange (THRIVE) and target-controlled infusion (TCI) intravenous anesthesia with propofol and remifentanyl. The laryngoscopy microsurgery operation will be divided into two groups: the group administrate muscle relaxants, and the group maintain spontaneous breathing without administering muscle relaxants.

After installing the monitor, Optiflow 100% 20L/min oxygen was used to pre-oxygenation through the nasal device for five minutes, and the patient was given intravenous injection of 0.2 mg glycopyrolate and 40 mg methylprednisolone and 5 mg midazolam.

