The second group: the group using muscle relaxants will first give a low dose of cisatracurium about 1.5-3mg, and after the effect of Propofol TCI loses consciousness, 0.6mg/kg Rocuronium or 0.1mg/kg Cisatracurium will be administered. When the patient stops breathing, Optiflow is adjusted to 50L/min and maintained until the end of the operation, the patient resumed spontaneous breathing. The patient's head will strengthen and ensure that the airway is stable, and the laryngeal

microscope will erect and reveal the location of the lesion to facilitate surgery. Low-dose muscle relaxant succinylcholine will be given continuously to maintain muscle relaxation until the end of the operation.

The third group: the group without the muscle relaxant will first touch the rear of the hyoid bone to the greater cornu about 0.5-1cm below the inner side of the greater hornu, that is, the internal branch of superior laryngeal n(chart I). Injection through the thyrohyoid membrane 1% Lidocaine 1-2ml for bilateral Superior laryngeal nerve block, and intravenous injection of Lidocaine 1-1.5mg/kg, Propofol TCI occurs.

(chart I)

The patient loses consciousness after setting up the laryngoscope, and 10% Lidocaine spray is used for intratracheal spray. After the effect is produced, the operation can be performed. Optiflow is adjusted to 50 L/min and maintain until the end of the operation.

After the operation, Propofol TCI and remifentanil TCI are stopped to wake up the patient, and Optiflow is adjusted to 15-20L/min. Patients who are given muscle relaxants will be given 1 mg of Atropine and 2.5 mg of neostigmine after spontaneous breathing is restored. After the patient resumes complete spontaneous breathing, Optiflow is stopped, the patient will be put on an oxygen mask, and transferred to a postanaesthesia care unit PACU for postoperative observation. After leaving the PACU, the patient will be transferred to the general ward to observe for one night.

Target-controlled infusion (TCI) injection of propofol will be set to Schneider model, Ce-targeted: 2.0-4.0 ug/ml, remifentanil 2–6 ng/ml. GE Entropy EasyFit Sensor was used to monitor intraoperative State Entropy (SE), Response Entropy (RE) and

Surgical plethysmographic index (SPI), and as a reference for adjusting TCI propofol and remifentanyl.

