Table VII. The surgeon was satisfied with the surgical satisfaction of the three groups, but the stress intensity was higher when performing non-intubation and nerve block surgery.

Table VIII. Dunnett T3 Post-hoc tests of during the operation

variable			M.D (I-J)	SE	p-value
pH_2	G1	G2	.135961*	.024404	.001
		G3	-.013455	.017469	.825
	G2	G1	-.135961*	.024404	.001
		G3	-.149416*	.024411	.000
	G3	G1	.013455	.017469	.825
		G2	.149416*	.024411	.000
PaCO2_2	G1	G2	-32.0468*	8.5162	.020
		G3	-1.1636	3.9766	.987
	G2	G1	32.0468*	8.5162	.020
		G3	30.8831*	8.8281	.023
	G3	G1	1.1636	3.9766	.987
		G2	-30.8831*	8.8281	.023
PaO2_2	G1	G2	-134.9130	52.1401	.087
		G3	-155.0273*	45.5545	.012
	G2	G1	134.9130	52.1401	.087
		G3	-20.1143	63.6399	.984
	G3	G1	155.0273*	45.5545	.012
		G2	20.1143	63.6399	.984

*. The M.D is significant at the 0.05 level.

[figure not shown]
Table VIII. Found the following situation :

1. In the non-intubated and muscle relaxant group (G2), the pH value during the operation was lower than the non-intubated and nerve-blocking group (G3), and lower than the normal value (7.35-7.45) .
2. During the operation, the PaCO2 of the non-intubated and muscle relaxant group (G2) was significantly higher than intubated group and also higher than the non-intubated and nerve-blocking group.
3. The PaO2 value of the intubation group (G1) during the operation was lower than that of the non-intubation group.

KSVGH20-C9-09 CASE REPORT

No:	Consent Signed _(MM/DD/YYYY) :	Operation Date:				
Patient status : _____						
Reason for quitting :						
Gender:	Age:	Weight _(kg) :	Height _(cm) :	BMI:	ASA:	
BASELINE MEDICAL/SURGICAL HISTORY :						
Time to enter the room :		Before induction BT:_____ SpO ₂ :_____ BP:___/___ PR:___ RR:___				
Study Group		Operation time				
Induction time		Anesthesia time				
Endo size & pressure		Propofol dose		Rocuronium dose		
		Fentanyl dose		Cisatracurium dose		
GAS		Before(:) G1: intubation ; G2: cis and scc ; G3: SLNB		OP end(:)		
pH				POR(:)		
PaCO ₂						
PaO ₂						
SO ₂ %						
HCO ₃ ⁻						
Time to post anesthesia recovery room :						
BT:_____ SpO ₂ :_____ BP:___/___ PR: ___ RR:_____						
PACU	Time	oxygen	respiration	circulation	consciousness	activity

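### PaO2 is tested between intubated and non-intubated groups without inspired oxygen stated for G1 or captured for any group, so the gap cannot be attributed to intubation itself

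*Protocol*

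**What the plan says.** The Results part of the summary says that 30 patients per group are needed to "compare the effects of intubation and non-intubation on the surgical field of vision and the changes in blood oxygen during the operation". Section C (Methods and Study Procedure) lists arterial blood gases at three times (before the airway or block procedure, at the end of the operation, and 15 minutes after arrival in recovery) and calls them a secondary result.

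Oxygen delivery is described unevenly in section C:

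- **G1 (intubated):** after intubation, "it will be transferred to the respirator for positive pressure ventilation and maintained until the end of the operation". No inspired fraction or oxygen flow is given, and no pre-oxygenation step is described.
- **G2 and G3 (non-intubated), before induction:** "Optiflow 100% 20L/min oxygen was used to pre-oxygenation through the nasal device for five minutes".
- **G2, during surgery:** "Optiflow is adjusted to 50L/min and maintained until the end of the operation".
- **G3, during surgery:** "Optiflow is adjusted to 50 L/min and maintain until the end of the operation".

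The blood-gas list in section C names PaO2, PaCO2, pH and HCO3. The case report form adds SO2 and, for the tube, its size and pressure. Neither has an entry for inspired oxygen. Section C says that anaesthesia records will be kept, but does not name inspired oxygen among the data or plan any use of it.

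Table II tests PaO2 across the three groups at each time, and Table VIII gives pairwise Dunnett T3 tests for the operative sample. The third conclusion under Table VIII reads: "The PaO2 value of the intubation group (G1) during the operation was lower than that of the non-intubation group".

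**The concern.** PaO2 depends directly on the inspired oxygen fraction. Two arms have a described high-flow source, given as 100% oxygen at pre-oxygenation, and the third has an unspecified ventilator setting. A raw PaO2 comparison between them therefore mixes airway technique with oxygen setting. An analysis plan cannot separate the two later if the fraction was never put into the study data.

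What is at stake is how one secondary comparison is read. Conclusion 3 carries no caveat and sits in a protocol that sets out to compare the effects of intubation and non-intubation. It also treats the non-intubated patients as one group, while the table above it tests G2 and G3 separately and does not give the same result for both.

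**Working it through.** **1. Reproducing Table VIII.** Inputs are the operative PaO2 means and SDs in Table II: G1 186.9 (64.0), n=11; G2 321.8 (128.2), n=7; G3 341.9 (136.9), n=11. SE = sqrt(s1²/n1 + s2²/n2), with Welch-Satterthwaite df and p from the studentized maximum modulus with three comparisons.

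| Pair | Difference | SE | df | p, recomputed | p, Table VIII |
|---|---|---|---|---|---|
| G1-G2 | -134.9 | sqrt(372.4 + 2347.9) = 52.2 | 7.9 | 0.088 | .087 |
| G1-G3 | -155.0 | sqrt(372.4 + 1703.8) = 45.6 | 14.2 | 0.012 | .012 |
| G2-G3 | -20.1 | sqrt(2347.9 + 1703.8) = 63.7 | 13.6 | 0.984 | .984 |

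The table is arithmetically sound. At the protocol's 0.05 level only G1-G3 is significant.

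**2. Pooling the non-intubated patients** (not done in the protocol). Mean = (7×321.8 + 11×341.9)/18 = 334.1, SD 130.1. The difference from G1 is 334.1 - 186.9 = 147.2, SE sqrt(64.0²/11 + 130.1²/18) = 36.2, Welch 95% CI about 73 to 222. The raw gap is real in these data. The open question is its cause.

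**3. How far inspired oxygen could account for it.** The documents give no G1 fraction, so this is a sensitivity range and not an estimate. Assume G2 and G3 were at 1.0.

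- *PaO2/FiO2.* The groups are equal when G1 is at 186.9/334.1 = 0.56. At 0.4 the G1 ratio is 186.9/0.4 = 467, above 334. At 1.0 it is 187, below 334.
- *Alveolar gas equation* (further assuming sea level and respiratory quotient 0.8): PAO2 = 713×FiO2 - PaCO2/0.8, with operative PaCO2 from Table II.
  - G2: 713 - 86.4/0.8 = 605.0, arterial/alveolar ratio 321.8/605.0 = 0.53.
  - G3: 713 - 55.5/0.8 = 643.6, ratio 341.9/643.6 = 0.53.
  - G1 at the same ratio would show 186.9 at FiO2 = (186.9/0.531 + 54.4/0.8)/713 = 0.59.
  - Expected G1 PaO2 at that ratio is about 115 at 0.4, 153 at 0.5, 191 at 0.6, 267 at 0.8 and 343 at 1.0.

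The protocol excludes none of these fractions.

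**4. Other differences in the protocol's own tables.**

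- *Before surgery (Table II):* PaO2 321.2 in G1 against 451.9 and 377.5, p=0.14. The pooled non-intubated mean is (7×451.9 + 11×377.5)/18 = 406.4, so G1 was already about 85 mmHg lower.
- *Change in group means to operation end:* G1 186.9 - 321.2 = -134.3; G2 321.8 - 451.9 = -130.1; G3 341.9 - 377.5 = -35.6. On this scale G1 and G2 are nearly alike.
- *Operation time (Table VI):* 77.4 minutes in G1 against 37.3 and 39.7, so the end-of-operation sample came later in G1.
- *Recovery (Table II):* 123.3, 110.8 and 116.3, p=0.77. The gap is gone once the operative oxygen sources are no longer in use. This fits an oxygen-source explanation but does not prove one.

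**The case against.** The other side has good points, and most of them stand.

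- **Conclusion 3 is a description.** A reader might infer that the protocol already claims better oxygenation from avoiding intubation. It does not: the sentence says only that a value was lower, which is true, and it claims neither cause nor significance.
- **PaO2 is not a target of the trial.** A reader might take the stated aim about blood oxygen to mean oxygenation. The protocol uses that term for the whole gas panel (Table II's title covers pH, PaCO2 and HCO3 as well), takes the gases mainly to study pCO2, and calls them secondary. None of Ho1 to Ho5 and none of the second-year primary outcomes concerns PaO2.
- **The fraction may exist.** It would go too far to say that inspired oxygen is unrecorded. Anaesthesia records are kept and may hold it. What is missing is a study data field and a plan to use it.
- **Bias is not demonstrated.** A reader might infer that a lower ventilator setting produced the gap. The 0.56 and 0.59 are solved backwards from equality. A ventilator setting cannot explain a deficit present before intubation, although unequal pre-oxygenation might.
- **Raw PaO2 is a legitimate package contrast.** High-flow oxygen is part of the non-intubated technique, the delivered fraction under it is approximate, and a simple PaO2/FiO2 ratio ignores the much higher PaCO2 in G2.
- **Saturation hardly differed during surgery:** SO2 99.3 to 99.7% (p=0.48).

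These points limit the consequence, but they do not repair the comparison. PaO2 is tested and reported, without a caveat, in a form that cannot separate airway technique from oxygen delivery.

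**Conclusion.** The point holds as a minor one. The operation-end gap of 135 mmHg (G1-G2) to 155 mmHg (G1-G3) is correctly calculated but cannot be attributed to intubation itself. With G2 and G3 assumed at a fraction of 1.0, an unknown G1 fraction between 0.4 and 1.0 moves G1 from a better to a worse PaO2/FiO2 than the non-intubated patients, with equality near 0.56 (0.59 by the alveolar gas equation). Lower PaO2 before intubation and longer operations in G1 are further unresolved explanations.

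Conclusion 3 is true of the point estimates, and a pooled test would support it. The table it summarises, however, reaches significance only for G1-G3, and the conclusion does not say so. Neither the primary outcomes nor the CO2 comparison is affected.

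**What to change.** 1. **Form:** add a field for the set inspired oxygen fraction and flow at each of the three blood gases, in all groups. Complete it from the anaesthesia record where that holds the value, including for the 29 patients already enrolled. The protocol still expects 61 more, so most of the data can be collected prospectively.
2. **Analysis:** report between-group PaO2 as a descriptive contrast of whole anaesthetic packages, including their oxygen delivery. Use PaO2/FiO2 only as a supportive analysis, noting that the delivered fraction under nasal high flow is approximate.
3. **Conclusion 3:** state that oxygen settings were not matched or captured, and give the pairwise p-values (.087 for G1-G2, .012 for G1-G3) in place of a statement about the non-intubated patients as a whole.

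The cost is a small form addition, some transcription and a wording change. No oxygen setting is proposed.

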Laryngoscope microsurgery (laryngomicrosurgery, LMS) is one of the most common otolaryngology procedures, mainly used to remove vocal cord polyps, nodules or cysts, laryngeal granuloma, or laryngeal papillomas, vocal cord plastic surgery, dipper-like Cartilage reduction, or fixation, etc. Traditional laryngoscope microsurgery requires general anesthesia for tracheal intubation, mainly because the endotracheal tube can provide a stable gas exchange airway. However, general anesthesia with endotracheal intubation requires the use of muscle relaxants, which may lead to the risk of postoperative pulmonary complications(1) and tracheal intubation may cause postoperative throat discomfort and pain (2,3)

Transnasal humidified rapid-insufflation ventilator exchange (THRIVE) is a physiological device that can provide heated 50-70L / min humidified oxygen. Cavity and provide a degree of continuous positive airway pressure.(4)

Since the development of the transnasal humidified rapid-insufflation ventilator exchange (THRIVE), because of the ability to provide an effective oxygen supply to patients without intubation anesthesia, many traditional intubation general anesthesia operations have to be performed without intubation (5) . The best way to use the nasal humidification rapid inflation exchange ventilation device is that the patient maintain self-breathing function and has a better gas exchange effect(6). If the patient is given a muscle relaxant or temporarily stopped breathing, it is difficult to completely avoid carbon dioxide retention and hypercapnia. (7,8)

Traditional laryngoscopy microsurgery requires endotracheal intubation anesthesia, which may lead to obstruction of the surgical field of vision and the inability to check the vocal cords completely. Transnasal humidified rapid-insufflation ventilator exchange (THRIVE) Optiflow can provide oxygenation to increase the success rate of laryngoscope microsurgery for non-intubation anesthesia patients (5), and Provide

excellent surgical vision and complete inspection of the vocal cords. Muscle relaxants are used during surgery to avoid reflexes such as coughing caused by vocal cords and throat irritation. The use of muscle relaxants during this time will cause the patient to apnea.

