During the operation, a pulse oximeter will be used to monitor and record the patient's oxygen saturation. The patient's gender, height, weight, BMI, age, past medical history, ASA classification, type of laryngoscopic surgery, operation time, lesion location, blood loss, and anesthesia records will be kept.

All three groups of patients will use radial artery catheters. In addition, the three groups performed arterial blood gas analysis (including: PaO₂, PaCO₂, pH, HCO₃⁻) at the following times to understand the difference of pCO₂ in different groups and as a secondary result.

The first period to measure those variables is before each set of surgery are follows:

The first group is before tracheal intubation.

The second group was before the administration of muscle relaxants.

The third group is before applying superior laryngeal nerve block bilaterally.

The second period to measure those variables is the end of the operation.

The third period to measure those variables is 15 minutes after entering the recovery room.

All the anesthesia time, operation start time and operation end time of the three groups will be recorded, and the relationship between them will be discussed.

After the operation, the surgeon and the patient will be asked to do a questionnaire survey in order to understand whether the non-intubation anesthesia laryngoscope microsurgery of the self-breathing causes obstruction or other difficulties for the operator, as well as the patient's postoperative recovery, surgical satisfaction and operation After scoring. Finally, the surgeon's score on the degree of surgical completion was taken as the primary outcome.

Conditions for participating in this research project:

- Subjects are between 20-80 years old.
- Patients undergoing laryngoscope microsurgery.

- Anesthesiologists rated ASA as between I and III.

If those who are included have any of the following conditions, you will not be able to participate in this research project:

- Having drug dependence and drinking habits.
- Abnormal heart, liver and kidney function.
- Allergic reactions to narcotic drugs.
- Emergency surgery.
- pregnancy.
- Refuse to participate.

This study will explore the following assumptions:

Ho1: The intraoperative field of vision of the nonintubation group is clearer than that of the intubation group.

Ho2: Non-intubation and no muscle relaxation has less carbon dioxide retention and less hypercapnia.

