NBPd	83.8	9.7	83.3	9.1	71.6	14.5	0.06
PR	69.8	7.5	71.4	16.0	72.3	10.2	0.46
RR	14.7	2.9	15.6	4.0	15.8	2.6	0.79
In surgery							
SpO2	98.4	1.0	98.1	1.8	97.9	2.2	0.96
NBPs	128.7	19.7	133.3	16.2	123.8	16.4	0.45
NBPd	80.2	11.4	72.9	9.2	71.4	10.2	0.15
HR	83.8	15.1	90.4	9.6	88.4	13.3	0.54
After surgery							
BT	36.2	0.5	36.0	0.1	36.0	0.4	0.26
SpO2	98.9	1.4	98.9	1.1	98.3	2.3	0.85
NBPs	138.5	26.5	117.0	13.4	124.4	6.4	0.20
NBPd	85.5	16.8	77.3	14.8	78.0	8.5	0.26
PR	83.5	6.6	81.1	12.6	89.1	13.2	0.46
RR	15.4	3.0	16.1	4.0	15.8	2.8	0.63
PAR Score	8.8	1.7	7.1	2.1	7.8	2.1	0.15

Table V. The heartbeat of group 2 tends to rise during the operation

Table VI. Operation status

Variable	G1(n=11)		G2(n=7)		G3(n=11)		p-value
	Mean	SD	Mean	SD	Mean	SD	
OP time	77.4	35.8	37.3	8.1	39.7	21.4	0.00
	n	(%)	n	(%)	n	(%)	
LMS Procedures							
Vocal polyp	1.0	9.1	1.0	14.3	3.0	27.3	0.14
Vocal cyst	4.0	36.4	2.0	28.6	0.0	0.0	
Vocal atrophy	1.0	9.1	2.0	28.6	0.0	0.0	
Vocal paralysis	0.0	0.0	0.0	0.0	0.0	0.0	
Laryngeal tumor	1.0	9.1	0.0	0.0	0.0	0.0	
Other	4.0	36.4	2.0	28.6	8.0	72.7	
Lesion site							
Ant.	3.0	27.3	0.0	0.0	0.0	0.0	0.16
Middle	4.0	36.4	3.0	42.9	5.0	45.5	
Post.	1.0	9.1	0.0	0.0	2.0	18.2	
Mixed	1.0	9.1	0.0	0.0	0.0	0.0	
Ant & Middle	2.0	18.2	1.0	14.3	0.0	0.0	
other	0.0	0.0	3.0	42.9	4.0	36.4	
Surgery completion							
Complete	11.0	100.0	7.0	100.0	11.0	100.0	N/A
Partially complete	0.0	0.0	0.0	0.0	0.0	0.0	
Incomplete	0.0	0.0	0.0	0.0	0.0	0.0	
Vision							
Good	10.0	0.9	7.0	100.0	10.0	0.9	0.71
Poor	1.0	0.1	0.0	0.0	1.0	0.1	
Poor Visualization							
none	10.0	90.9	7.0	100.0	10.0	90.9	0.51
Difficulty with vocal cord injection	0.0	0.0	0.0	0.0	1.0	9.1	
Other	1.0	9.1	0.0	0.0	0.0	0.0	
The Cormack-Lehane (CL) glottis view classification							
I	9.0	81.8	6.0	85.7	9.0	81.8	0.97
IIa	2.0	18.2	1.0	14.3	2.0	18.2	
IIb	0.0	0.0	0.0	0.0	0.0	0.0	
III	0.0	0.0	0.0	0.0	0.0	0.0	
IV	0.0	0.0	0.0	0.0	0.0	0.0	
Laryngeal compress							
Not applied	1.0	9.1	0.0	0.0	0.0	0.0	0.43
Applied	10.0	90.9	7.0	100.0	11.0	100.0	
N/A : Not suitable for any statistics.							

Table VI. Among the three groups of operation time, the operation time of the first

group was longer than that of the other two groups.

Table VII. Surgeon's Feedback

Variable	G1(n=11)		G2(n=7)		G3(n=11)		p-value
	n	(%)	n	(%)	n	(%)	
Satisfaction							
Satisfied	11.0	100.0	7.0	100.0	10.0	90.9	0.43
Partially satisfied	0.0	0.0	0.0	0.0	1.0	9.1	
Unsatisfied	0.0	0.0	0.0	0.0	0.0	0.0	
	Mean	SD	Mean	SD	Mean	SD	
Stress index	1.0	0.0	1.9	1.2	2.0	0.8	0.01

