i:oxygen saturation 2: able to maintain oxygen saturation >92% on room air; 1: needed oxygen inhalation to maintain oxygen saturation >90%; 0: oxygen saturation <90% even with oxygen supplement ii:respiration 2: able to breathe deeply and cough freely; 1: dyspnea or limited breathing; 0: apneic iii:circulation 2: blood pressure ±20% of preanesthetic level; 1: blood pressure from ±20% to 49% of preanesthetic level; 0: blood pressure ±50% of preanesthetic level iv:consciousness 2: fully awake; 1: arousable on calling; 0: not responding v:activity 2: able to move 4 extremities voluntarily or on command; 1: able to move 2 extremities voluntarily or on command; 0: unable to move extremities voluntarily or on command						

Surgical records

	Ant.	Middle	Post.	Mixed	
Lesion site					
	Vocal polyp	Vocal cyst	Vocal atrophy	Vocal paralysis	Laryngeal tumor Bx
LMS Procedures					
Surgery completion	 Complete		 Partially complete		 Incomplete
Satisfaction	 Satisfied		 Partially satisfied		 Unsatisfied
Vision	 Good		 Poor		
Poor Visualization	 Inability to suppress gag reflex  Inability to achieve anesthesia  Had to change approach  Others:		 Copious secretions  Difficulty with vocal cord injection		
The Cormack-Lehane (CL) glottis view classification  I  IIa  IIb  III  IV					
					
Laryngeal compress :  Not applied  Applied					
Stress index  1  2  3  4  5					
Other :					

Postoperative evaluation

I. Evaluation (Score : none=1,minor=2,moderate=3,severe=4) , **time** :

- Sore throat : _____
- Hoarseness : _____
- Swallowing difficulty : _____
- Breathing difficulty : _____

II. Ward recording (24hr postoperative event) :

Score	Nausea()	Vomiting()	Nausea/vomiting()
0	none	none	none
1	minor	minor	minor
2	moderate	moderate	moderate
3	severe	severe	severe

D EXPECTED WORK ITEMS AND SPECIFIC RESULTS

Projects expected to be completed in the second year

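### The case report form's procedure list leaves 14 of 29 operations (8 of 11 in group 3) as an unexplained Other, so procedure balance between the groups cannot be judged from Table VI

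*Protocol*

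**What the plan says.** Section B (Background and Purpose) describes what laryngomicrosurgery is mainly used for: "vocal cord polyps, nodules or cysts, laryngeal granuloma, or laryngeal papillomas, vocal cord plastic surgery, dipper-like Cartilage reduction, or fixation". The list is open-ended.

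Section C (Methods and Study Procedure) says that the study will keep "type of laryngoscopic surgery, operation time, lesion location" among other items. It gives no further purpose for the procedure and site data. It says only that patients are divided into three groups and describes no random allocation.

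The case report form (Surgical records) offers these procedures: "Vocal polyp Vocal cyst Vocal atrophy Vocal paralysis Laryngeal tumor Bx". The last named option is "Laryngeal tumor Bx". For lesion site it offers: "Ant. Middle Post. Mixed". A free-text line for other remarks closes the surgical record.

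Table VI (first 29 patients) reports procedures with the row "Other 4.0 36.4 2.0 28.6 8.0 72.7" and p = 0.14 for the whole block. For lesion site it adds *Ant & Middle* and *other* to the form's four sites, with p = 0.16. It also records one group 3 patient under "Difficulty with vocal cord injection".

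**The concern.** Type of operation and lesion site may affect how long surgery takes and how well the surgeon sees, whatever the anaesthetic. The protocol compares the groups on exactly these matters. Its first hypothesis concerns the surgical view, its fifth concerns suitability for longer operations, and Table VI contrasts mean operation times of 77.4, 37.3 and 39.7 minutes.

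Without described randomisation, the tabulated case mix is the reader's main protection against confounding by procedure. The groups already differ at baseline on ASA class (printed p = 0.04). If nearly half the operations, and most of those in group 3, sit in one unspecified category, that protection is missing. A p-value of 0.14 beside the block could be taken as a sign of comparability that it does not give.

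**Working it through.** **1. Form against section B.** Polyp and cyst have boxes. Vocal cord plastic surgery might be entered under atrophy or paralysis, and papilloma under tumour. Nodule, granuloma and cartilage reduction or fixation have no evident box, and neither does injection. In group 3 the only named procedure used is polyp (3 of 11), so the patient with the injection difficulty was coded either polyp or Other.

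**2. Counts from Table VI.**

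| Procedure | G1 (11) | G2 (7) | G3 (11) | Total |
|---|---|---|---|---|
| Polyp | 1 | 1 | 3 | 5 |
| Cyst | 4 | 2 | 0 | 6 |
| Atrophy | 1 | 2 | 0 | 3 |
| Paralysis | 0 | 0 | 0 | 0 |
| Tumour | 1 | 0 | 0 | 1 |
| Other | 4 | 2 | 8 | 14 |

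Other: (4 + 2 + 8)/29 = 14/29 = 48.3%. By group: 4/11 = 36.4%, 2/7 = 28.6%, 8/11 = 72.7%, as printed. A like-for-like comparison that includes group 3 has only the polyp row: 1, 1 and 3 patients.

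**3. Reproducing p = 0.14.** Drop the empty paralysis row. Expected count = row total × column total / 29, and chi-square = sum of (observed − expected)²/expected. The row contributions are polyp 1.10, cyst 3.79, atrophy 3.40, tumour 1.64 and Other 2.25, which sum to 12.18. With (5 − 1) × (3 − 1) = 8 degrees of freedom, p = 0.143, matching the printed 0.14. Only two expected counts reach 5 (Other in groups 1 and 3, each 14 × 11/29 = 5.31), so 13 of 15 are below 5. An exact (Fisher-Freeman-Halton) test by 20,000 permutations gives about 0.08.

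**4. How far recoding could move the result.** The documents do not say what the 14 operations were, so these splits are assumptions:

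| Assumed make-up of Other | Pearson p |
|---|---|
| Two types, same proportions in every group | 0.27 |
| One type in groups 1 and 2, another in group 3 | 0.003 |
| A different type in each group | 0.0003 |

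The present coding is compatible with anything from no visible imbalance to a gross one.

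**5. Lesion site.** *other* holds 0 + 3 + 4 = 7 of 29 (24.1%). *Ant & Middle* holds 2 + 1 + 0 = 3 and *Mixed* holds 1. A lesion that is both anterior and middle fits either label, so the two overlap. The printed p = 0.16 reproduces (chi-square 14.30, 10 degrees of freedom, p = 0.160), but all 18 expected counts are below 5. The exact p is about 0.09.

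**6. Entries to recode.** 14 procedures + 7 *other* sites + 3 *Ant & Middle* sites = 24 at most.

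**The case against.** The strongest reply is that this is an incomplete interim tabulation and contradicts nothing in the protocol. Several parts of that reply stand.

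- **Purpose.** A reader might infer that Table VI is meant to show comparable case mix and cannot detect a difference. The protocol says only that the items are recorded and never cites p = 0.14 as evidence of balance. The uneven Other share (36%, 29%, 73%) is visible in the table.
- **Cause.** A reader might infer that the missing boxes produced the 48%. Section B gives general background, not a list of trial operations, and the 14 cases are not described.
- **Site codes.** It is tempting to count the *Ant & Middle* cases as off the form too, giving 10 of 29. Marking two printed columns could produce that label, so only the 7 *other* sites clearly fall outside the four sites. The form was read from a PDF and has a free-text line, so no missing Other box can be claimed.
- **Group 3 against the rest.** Pooling groups 1 and 2 gives 8/11 against 6/18, Fisher p = 0.06, but that pooling follows a look at the data. The three-group test of Other against named procedures gives p = 0.11 (exact about 0.16).
- **Operation time.** Groups 1 and 2 have similar Other shares (36% and 29%) and identical cyst shares to these (36% and 29%), yet took 77.4 and 37.3 minutes. Groups 2 and 3 differ most in Other (29% and 73%), yet took 37.3 and 39.7. The documents therefore do not show that procedure mix explains the long times in group 1. This does not rule it out either, because the contents of Other in each group are unknown.
- **Recoverability.** The type of surgery is kept on record, so an adjusted comparison is not out of reach once the cases are recoded. The choice of covariates may properly sit in a statistical analysis plan that is not shown here.

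What remains is that the coding, as tabulated, does not say what was done in about half the patients, and an analysis plan cannot supply categories that were never coded.

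**Conclusion.** The point holds in a limited form. The procedure list does not match the range of operations given in section B. Of the first 29 procedures, 14 (48%), and 8 of 11 in group 3, are unclassified. Seven of 29 sites are likewise unclassified, and two site labels overlap. Procedure balance therefore cannot be judged from Table VI, and p = 0.14 gives no reassurance either way.

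The counts and tests need no assumption beyond the printed table. The importance of the point rests on two premises: that allocation is not random, since none is described, and that procedure type can influence operation time. The documents do not establish that the short list caused the high Other share, that case mix explains the operation-time gap, or that either second-year primary outcome (carbon dioxide retention, lung complications) is affected. Adjustment would also add nothing for completion (29 of 29 complete) and very little for vision (2 poor of 29). This is a minor point, worth acting on because 61 of the planned 90 patients are still to come.

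**What to change.** For the remaining patients, extend the form's procedure list to the operations named in section B plus vocal cord injection, with an *other* option that must be specified. Replace the site list with one non-overlapping code, for example anterior, middle, posterior, more than one, or not on the cord.

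For the 29 patients already entered, recode the 14 Other procedures and the 7 *other* and 3 *Ant & Middle* sites from the operation records.

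In the analysis, define a coarse procedure class of two or three levels and include it as a covariate or stratum in the group comparison of operation time. Tabulate vision by class without modelling it.

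The cost is a form revision, chart recoding of at most 24 entries and a little extra analysis. The limitation is that 30 patients per group will support only a few classes, so some mixing of procedures within a class will remain.
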